2.4 Study Hypothesis

The primary hypothesis of this study is that in addition to SoC, AB103 will demonstrate a clinically significant treatment benefit over placebo.

This hypothesis will be addressed by measuring the effect of AB103 on a composite of clinical parameters associated with the disease course of patients with NSTI, using a responder analysis. A responding patient must meet all the 5 parameters of the composite clinical success end point, while a non-responding patient can fail by not meeting any one of the parameters. These analyses are designed to demonstrate that in addition to being safe, one dose of 0.5 mg/kg of AB103 will:

Improve systemic signs of the infection by improving organ function of patients compared to placebo as measured by:

- Survival at Day 28
- mSOFA score on Day 14 and change from baseline to Day 14 ≥ 3. Day 14 mSOFA score of ≤1 and a change from baseline (pre-treatment) to Day 14 ≥3 will be required for a patient to achieve the primary composite clinical success endpoint (NICCE)

Improve the local signs of the infection, as measured by:

- Reduced number of debridements, counted to Day 14. No more than 3 debridements to Day 14 will be required for a patient to achieve composite clinical success
- No amputation after the first debridement (amputation on the first debridement is not considered a failure). A patient will be required to have had no amputations done after the first surgical procedure in order to achieve composite clinical success.

A full response will be considered as meeting **all** the above systemic and local criteria for response, in addition to being alive at Day 28.

A conditional co-primary endpoint will be evaluated only if the two-sided p-value for the primary responder analysis is ≤ 0.01 .

The conditional co-primary endpoint also involves a responder analysis that involves being alive at Day 28 and demonstrating improvement in the local signs of infection as measured by:

- A reduced number of debridements, counted to Day 14. A patient with ≤3 debridements to Day 14 will be considered a responding patient
- No amputation after the first debridement (amputation during the first debridement is not considered a failure). A patient with no amputations performed after the first surgical procedure will be considered a responding patient in relation to this parameter.

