4.3.2 Visit 2 (Day 1)

Starts ONLY upon study drug administration and terminates at the end of the calendar day. Study drug may be given either during surgery or immediately after the surgery.

- Drug administration should be completed within 6 hours from the clinical diagnosis of NSTI and a decision at the study site for urgent surgical wound exploration and debridement
- Collect data on operative procedures(see Section 6.2.6.1 for description of adjudication of operative procedures for assignment of study defined debridement)
- Collect data on acute renal replacement therapy
- Collect data on plasma or platelet transfusion
- Collection of AEs/ SAEs
- Concomitant medications
- Vital signs (first set of vitals on that day)
- Symptom-driven interim PE
- 12-Lead ECG at the end of study drug infusion, at 4-6 hours and 12-24 hours post administration of study drug
- Urine output (should be recorded continuously from time of ICU admission to Day 7, if still in ICU and Foley catheter in place, using 6 hour intervals and by calendar day)
- Weight, only if not collected at screening
- Collect data on additional amputations
- Critical care parameters (dates and times of assisted ventilation, vasopressor use, ICU /hospital stay)
- Systemic response: mSOFA score. Measurements will be collected within 16-24 hours post study drug administration, unless the patient is scheduled to undergo additional debridement; in such case data collection for mSOFA parameters will be taken prior to the next debridement
 - All efforts should be made to obtain the actual measurements of SOFA parameters at these visits-may use SpO2 value (and record FiO2) if arterial blood gas is not clinically indicated
 - Obtain serum creatinine
 - Obtain CBC with differential and platelet count (sample can be same as that required to be taken in conjunction with the RNA expression profile test sample)
- Assess lesion status (healing/progression/significant change in appearance) if accessible for visible assessment at time of debridement or routine dressing change

- Collect whole blood for leukocyte transcriptome (RNA expression) profiling at 4-6 hours post study drug dose
- Survival

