6.2.14 Total blood volume collected

The total maximal volume of blood to be collected in the study is composed of study specific tests as well as tests that are part of the SoC. The list below represents the combined blood quantities. Less than a unit of blood (12.5 tablespoons) will be collected for each patient.

Visit	Туре	Maximal
		Volume (cc)
1 SCR	CRP	3
	Chemistry	4
	Hematology	4
	Arterial Blood Gas*	2
	Pregnancy test	2
	Blood Culture	20
	AKI Biomarker	5
	Blood leukocyte transcriptome profile	5
	Immunogenicity sample	6
	Total Volume	52
	Hematology (CBC with differential and platelets)	4
	Arterial Blood Gas*	2
2 Day 1	Creatinine & Hematology (For SOFA calculation 16-24h post study drug administration)	7
	Blood leukocyte transcriptome profile (4-6 hour post study drug administration sample)	5
	Total Volume	18
	AKI biomarker	5
3 Day 2	Blood leukocyte transcriptome profile	5
	Arterial Blood Gas*	2
	Chemistry (only Creatinine)	3
	Hematology (CBC with differential and platelets-)	4
5	Hematology (only platelet count)-obtain if full CBC to be done with	4
	transcriptome sample is not performed on same calendar day as	
	study Day 2	
	Total Volume	23
4 Day 3	Chemistry (only Creatinine)	3
	Hematology (CBC with differential and platelets-can be used for	4
	mSOFA data and for the transcriptome)	2
	Arterial Blood Gas*	2

Table 6: Maximal Blood Drawing by Visit

Visit	Туре	Maximal
		Volume (cc)
	Blood leukocyte transcriptome profile	5
	Total Volume	14
	Chemistry	4
	Hematology (CBC with differential and platelets)	4
5	Arterial Blood Gas*	2
Day 7	AKI biomarker	5
	Blood leukocyte transcriptome profile	5
	Total Volume	20
	Arterial Blood Gas*	2
6	Chemistry (only Creatinine)	3
Day 10	Hematology (Platelets only)	4
	Total Volume	9
	Arterial Blood Gas*	2
	CRP	3
7	Chemistry	4
Day 14	Hematology (CBC with differential and platelets)	4
	Immunogenicity sample	6
	Total Volume	19
8	Arterial Blood Gas*	2
Day 21	Chemistry (only Creatinine)	3
	Hematology (Platelets only)	4
	Total Volume	9
9	Arterial Blood Gas*	2
Day 29	Chemistry (only Creatinine & Albumin)	3
	Hematology (CBC with differential and platelets)	4
	Immunogenicity sample	6
	Total Volume	15
10	Chemistry (only Creatinine)	3
Month	Immunogenicity sample	6
3	Total Volume	9
Total Study		188

* Obtain ABG if clinically indicated. Otherwise record SpO2 value and also FiO2.

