5.2.1 Mean and Mean Changes Over Time

Mean values (SD) for the mSOFA and for the 5 specific organ components will be summarized over time with and without last-observation-carried-forward (LOCF). Similarly, mean (SD) changes scores from both day 0 and day 1 will be summarized with and without LOCF.

5.2.2 mSOFA as Part of Primary Endpoint

The primary efficacy endpoint (NICCE) employs mSOFA in two of its five components. NICCE success requires mSOFA at Day $14 \le 1$ and the improvement from screening Day 0 to Day 14 that is ≥ 3 .

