5.8 Analysis of Longitudinal Outcomes

Supporting analysis will be performed for mSOFA over time using the Mixed Model for Repeated Measures (MMRM) analysis of covariance (ANCOVA) approach¹⁷. The following baseline covariates will be included in the primary MMRM analysis to mSOFA over time.

- Day 0 mSOFA = 3-4 versus > 4
- Presence versus absence of Fournier's gangrene
- APACHE II score
- mSOFA Day 1
- Presence of Stage 2/3 AKI at Screening

mSOFA Day 1 is included because this score reflects patient status post initial surgery. In addition to this variable, the Day 0 stratification factors are included to reflect the experimental design. Screening APACHE II is included to account for variation in medical status at screening. Presence of Stage 2/3 AKI at screening is included given emerging evidence of its impact on clinical outcomes. Inclusion of covariates can increase power by explaining variance and also help with the implicit imputation of missing values that is inherent in the MMRM approach.

MMRM is a direct likelihood approach that requires specialized statistical software for optimizing the likelihood function. For this study, all MMRM parameters will be estimated using SAS PROC MIXED [SAS Institute¹⁸]. The MMRM model is notable for its ability to include all available data from all eligible subjects and does not require their exclusion as in 'complete case analysis'

¹⁵ Cohen, J. Statistical power analysis for the behavioral sciences (2nd ed.). New York, Academic Press, 1988.

¹⁶ Verbeke G and Molenberghs G. Linear Mixed Models for Longitudinal Data, New York: Springer, 2000.

¹⁷ Verbeke G and Molenberghs G. Linear Mixed Models for Longitudinal Data, New York: Springer, 2000.

¹⁸ SAS Institute, Cary NC.

or arbitrary assignment of values as in 'last-observation-carried-forward' (LOCF). The MMRM model generally includes a factor for treatment group by time interaction in order to allow group differences in mean value to vary over time. Inclusion of outcome data from all time points informs the implicit imputation of values missing at specific time points through the outcome covariance matrix. Inclusion of baseline covariates has potential for further reduction of potential bias due from missing values.

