8.6 Distribution of mSOFA scores Over Time

Table 14.2.2.1 summarizes mSOFA and its 5 components over time, from screening to Day 28. Since bilirubin is collected only at screening and at Day 7 and 14, observed SOFA total scores will also be summarized at these three timepoints.

Table 14.2.2.2 provides the same summary after application of last-value-carried forward (LOCF) to Day 14. LOCF was not applied after patient death or for missing Day 21 or Day 28 mSOFA.

Table 14.2.2.3 summarizes changes from Day 0 in mSOFA and in each of its components to Days 1, 2, 3, 7, 10, 14, 21, and 28 without applying LOCF.

Table 14.2.2.4 provides the same summary after application of LOCF to Day 14. This table only summarizes mSOFA to Day 14 because there was no LOCF imputation for missing mSOFA after Day 14 and so the results for Days 21 and 28 are identical to the table summarizing mSOFA without LOCF.

Tables 14.2.2.5 and 14.2.2.6 provides the same summaries for observed and LOCF imputed mSOFA and components to Days 28 and 14, respectively, but for changes from Day 1 rather than Day 0.

The data displayed in Tables 14.2.2.1 to 14.2.2.6 will be graphically displayed in line plots comparing between treatment groups using line plot (Figures 5 to 10) and box and whiskers plots (Figures 11 to 14).

Table 14.2.2.7 will summarize mSOFA and organ specific values at screening, 16 - 24 hours post dose, and changes from screening to 16 - 24 hours post dose.

Table 14.2.2.8 will summarize mSOFA without the Glasgow Coma Score and without the Glasgow Coma Score Among Patients on Ventilation and Medications Affecting GCS to Day 28.

8.7 Time to resolution of mSOFA score to ≤ 1

Life tables for time to resolution of mSOFA score ≤ 1 will be provided in Tables 14.2.3.1 and 14.2.3.2 for the 0.50 mg/kg and placebo treated groups, respectively, to Day 14. Comparative Kaplan-Meier survival curves will be provided in Figure 15.

For these analyses, patients who die prior to Day 14 will be considered censored at one day past Day 14 and assumed to have never achieved mSOFA \leq 1. Log rank statistic will be used to assess if the distributions of times to symptom resolution differ between treatment groups.

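### The supporting mSOFA mixed model adjusts for Day 1 mSOFA as a baseline covariate although it is measured after dosing, so its Day 14 contrast is biased for the total treatment effect if the drug acts by Day 1

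*SAP*

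**What the plan says.** SAP 5.8 introduces the covariate list with "The following baseline covariates will be included in the primary MMRM analysis to mSOFA over time". The list has five entries: Day 0 mSOFA as 3-4 versus above 4, Fournier's status, APACHE II, Day 1 mSOFA, and Stage 2/3 AKI at screening. The reason given for the fourth is that "mSOFA Day 1 is included because this score reflects patient status post initial surgery". The same section gives the Day 14 contrast the most weight.

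Protocol 4.3.2 says of the Day 1 visit: "Starts ONLY upon study drug administration and terminates at the end of the calendar day". On the score itself it says: "Measurements will be collected within 16-24 hours post study drug administration, unless the patient is scheduled to undergo additional debridement". In that exception the score is taken before the next debridement, which is still after dosing. Protocol 6.2.14, Table 6, labels the Day 1 sample "For SOFA calculation 16-24h post study drug administration". SAP 8.6 tabulates the score at that time, with "changes from screening to 16 - 24 hours post dose", as an outcome by treatment group.

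Elsewhere baseline is pre-dose. Protocol 2.4 requires "a change from baseline (pre-treatment) to Day 14", and SAP 5.2.2 defines the NICCE component as "the improvement from screening Day 0 to Day 14". SAP 6.1 counts adverse events with onset from Day 1 as treatment-emergent.

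**The concern.** A covariate measured after dosing can carry part of the treatment effect. When that covariate is an early value of the outcome itself, adjusting for it changes what the Day 14 contrast estimates. It becomes a difference conditional on Day 1 status instead of the total effect of assignment to the drug. Randomization does not protect that conditional comparison.

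The surgical rationale does not remove the problem. Protocol 4.3.2 has the drug given during or immediately after the first surgery, so the Day 1 score reflects surgery and drug together.

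No version of the model restricted to pre-dose covariates is clearly specified. Protocol 9.2.9 mentions the outcome's baseline value, if appropriate, but SAP section 1 says the SAP prevails where the two differ. SAP 5.8 later refers to a baseline value without defining it, and SAP 8.8 does not give the covariates behind Figures 17 and 18. SAP 5.8 also does not say whether Day 1 mSOFA enters as one main effect or with a separate slope at each visit, and this changes the size of the bias.

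**Working it through.** **Timing.** The Day 1 visit begins at dosing (Protocol 4.3.2), and every permitted time for the Day 1 score follows dosing. The variable is post-treatment whichever branch applies.

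**Plan's own figure.** The documents state no effect size, SD or power for this model, so there is nothing to reproduce. All magnitudes below rest on assumed inputs.

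**Formula.** Let δ14 be the total drug effect on Day 14 mSOFA, δ1 the effect on Day 1 mSOFA (positive = benefit), and β the fitted slope on Day 1 mSOFA.

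- Adjusted Day 14 contrast = δ14 − β·δ1
- Share of the effect removed = β·δ1/δ14

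The bias vanishes if δ1 = 0. It would also vanish if β = 0, which is implausible for repeated scores of one outcome.

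**Illustration.** Assume δ14 = 1 point, δ1 = 0.5, equal SDs, and a Day 1-Day 14 residual correlation ρ of 0.2, 0.4 or 0.6.

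- *Separate slope by visit:* β = ρ at Day 14, so the share removed is 0.2 × 0.5 = 10%, 0.4 × 0.5 = 20%, 0.6 × 0.5 = 30%.
- *One main effect, correlation constant over visits:* β = ρ, giving the same 10/20/30%.
- *One main effect, correlation decaying with time:* β is pooled over visits as 1′V⁻¹r / 1′V⁻¹1. Here r holds the correlations of Day 1 with the later visits and V is the covariance of those visits given Day 1. With a constant part plus exponential decay (4-day constant) and visits at Days 2, 3, 7, 10 and 14, β = 0.62/0.74/0.84. The share removed is half of that: 31/37/42%. Extending the visits to Day 28 gives β = 0.54/0.70/0.82.

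**Multi-visit simulation.** Set-up: 145 per arm, SD 2, unstructured covariance, maximum likelihood, drug effect linear from δ1 at Day 1 to 1 at Day 14, missing-at-random dropout leaving 4-13% missing at Day 14, 200 runs per scenario, Monte Carlo error at most 0.02. Mean Day 14 estimates (true value 1), with triples for ρ = 0.2/0.4/0.6:

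| δ1 | Correlation | Day 1 as one main effect | Day 1 by visit | Day 1 as a response |
|---|---|---|---|---|
| 0.5 | constant | 0.91/0.81/0.70 | 0.91/0.81/0.70 | 0.98-1.02 |
| 0.5 | decaying | 0.72/0.63/0.56 | 0.92/0.80/0.68 | 0.98-1.02 |
| 0 | both | 0.97-1.02 | 0.97-1.02 | 0.97-1.02 |
| −0.5 (harm) | constant | 1.06/1.21/1.31 | 1.10/1.20/1.30 (formula) | 0.95-1.01 |
| −0.5 (harm) | decaying | 1.30/1.35/1.44 | 1.10/1.20/1.30 (formula) | 0.95-1.01 |

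**Shared unmeasured cause.** A separate single-visit check (145 per arm, complete data, 2,000 runs per scenario, negative = benefit) let an unmeasured factor affect both scores. Conditioning on Day 1 then adds a further term whenever the drug acts on Day 1.

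| Effect on Day 1 | Direct effect | Day 1 to Day 14 slope | Shared cause | True total | Adjusted for Day 1 | Screening score only |
|---|---|---|---|---|---|---|
| 0 | −0.5 | 0.6 | yes | −0.50 | −0.50 | −0.50 |
| −0.5 | −0.5 | 0.6 | no | −0.80 | −0.49 | −0.79 |
| −0.5 | −0.5 | 0.6 | yes | −0.80 | −0.25 | −0.80 |
| −1.0 | −0.5 | 0.6 | yes | −1.10 | 0.01 | −1.09 |
| −0.5 | 0 | 0.6 | yes | −0.30 | +0.24 | −0.30 |

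The loss can therefore be complete, or the sign can reverse.

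**Missing Day 1 scores.** SAP 5.10.1 fills a wholly missing day by last observation carried forward (LOCF), while SAP 5.2.4 keeps LOCF out of the MMRM data. If that exclusion also covers the covariate, which is an inference, patients with no Day 1 score drop out of the model. Each 1% would be 0.01 × 290 = 2.9 patients.

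**The case against.** The strongest objection concerns reach. SAP 5.7 and 5.8 make this model supporting and descriptive, and SAP 5.6 does not control type 1 error for it. NICCE, CCPE and the key secondary endpoint use unadjusted chi-square tests. Comparisons not adjusted for Day 1 are also planned: changes from Day 0 and time to resolution (SAP 8.6, 8.7) and the NICCE components (SAP 8.1). All of this stands, and it is why the point is not more serious.

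A second objection is that Day 1 is a disclosed reference point: SAP 5.8 gives a reason, and SAP 8.6 also tabulates changes from Day 1. A Day 1-conditional contrast can be reported, but it must be labelled as such. The SAP calls the covariate baseline, names no conditional estimand and clearly specifies no pre-dose alternative.

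Third, the size is assumption only. The multi-visit simulation used maximum likelihood where SAP 5.8 specifies REML, and the second check was a single-visit model. This is correct, and the percentages are illustrations. They are not bounds either: with δ1 = 0.5, δ14 = 0.25 and β = 0.6, the share removed is 0.6 × 0.5/0.25 = 120%.

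Finally, dropping the covariate costs precision, and if the drug does nothing by Day 1 that cost buys no reduction in bias. This is also true. It does not justify a contrast whose validity depends on an early effect that the plan does not rule out.

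**Conclusion.** The concern holds. Day 1 mSOFA is a post-dose value of the modelled outcome, and conditioning on it makes the Day 14 contrast biased for the total treatment effect unless the drug has no effect on mSOFA by Day 1 (or the Day 1 slope is zero). The direction follows from the sign of the early effect: early benefit is understated, and early harm is turned into apparent advantage.

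The size cannot be computed from the documents. Under the assumed inputs above, with δ1 at half of δ14, 10% to 42% of the effect is removed. Other plausible inputs remove all of it or reverse the sign. The damage is confined to one supporting analysis, and the trial's confirmatory conclusions do not depend on it. It should be corrected, because SAP 5.7 bases testing and estimation of mSOFA over time on this model.

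**What to change.** In SAP 5.8:

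- Remove Day 1 mSOFA from the covariates and include it as the first post-baseline response.
- Keep the pre-dose covariates: Day 0 mSOFA category, Fournier's status, APACHE II and screening Stage 2/3 AKI. Optionally add Day 0 mSOFA as a continuous score.
- Keep any Day 1-adjusted model only as a labelled sensitivity analysis, stating that it does not estimate the total effect and whether Day 1 enters as one main effect or by visit. State there how missing Day 1 scores are handled.
- State the covariates behind Figures 17 and 18.

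Separately, reconcile the Day 1 score timing in Protocol 4.3.2 with the 6 AM to noon window in the mSOFA footnote of Protocol Appendix A.

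The change is SAP wording and one model line. The cost is precision at Day 14. The standard error rises by the factor 1/√(1−ρ²) = 1.02/1.09/1.25 for ρ = 0.2/0.4/0.6. At ρ = 0.6 that equals 1/(1−0.36) = 1.56 times the patients for equal precision. In the multi-visit runs the change was +1% to +24% against by-visit entry and −7% to +24% against one main effect. The help with missing later visits that SAP 5.8 wants is kept, because Day 1 as a response still informs them through the covariance matrix. The change removes this bias only: the model still implicitly imputes mSOFA after death (SAP 5.10.1, 5.10.3).

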5.9 ITT vs mITT

A modified intent-to-treat (mITT) analysis set will be used in the primary and secondary evaluation of efficacy. This is due to the nature of the disease progression and necessity of surgical confirmatory diagnosis. It therefore cannot be avoided that there will be randomized subjects not belonging to the indicated population. These patients are excluded prior to receiving study medication but after randomization. For such patients their randomized allocation is re-used to preserve with strata balance but not their precise randomization ID to avoid confusion (see plan in Randomization section above).

Generally, the purpose of intent-to-treat (ITT) comparisons is to ensure that randomization is protected (i.e., all groups have comparable baseline characteristics and that any differences besides therapy are due to chance) and to preclude the possibility of bias due to selectively excluding subjects from therapy groups. This is intended to avoid systematic differences among the groups attributable to factors other than therapy assignment²⁴. Therefore, mITT comparisons will be according to randomized treatment assignment and we will attempt to include all mITT patients, regardless of intervention or length of follow-up in the primary efficacy comparison.

¹⁹ Burton P, Gurrin L, Sly P. Extending the simple linear regression model to account for correlated responses: An introduction to generalized estimating equations and multilevel mixed modelling. 2004. http://espace.library.ug.edu.au/view/UO:259851

²⁰ Diggle P, Heagerty P, Liang K-Y, Zeger S. Analysis of Longitudinal Data. Oxford University Press; 2002.

²¹ SAS Institute, Proc Mixed, SAS/STAT Software.

²² Hrong-Tai Fai A, Cornelius PL. Approximate F-tests of multiple degree of freedom hypotheses in generalized least squares analyses of unbalanced split-plot experiments. J Stat Comput Simul. 1996;54(4):363-378.

²³ Rubin DB. Inference and missing data. Biometrika. 1976;63(3):581-592.

²⁴ Knickerbocker R. Intent-to-Treat Analyses. In: Chow S-C, ed. *Encyclopedia of Biopharmaceutical Statistics*. Marcel Dekker; 2000.

5.10 Handling of Missing Data

5.10.1 mSOFA Scores

mSOFA scores will be assessed as 1) observed cases, 2) last observation carried forward (LOCF), 3) using MMRM, and 4) categorized and combined with mortality and local activity as part of the primary composite clinical success endpoint, NICCE.

The following will be defined as OBSERVED mSOFA.

- 1. If a single individual organ score is missing but other scores for that day are non-missing, the organ system that were not evaluated are assumed to be free of organ failure are given a value of zero when determining the sum score.
- 2. If two or more individual organ scores are missing for mSOFA on Day 14 or earlier, but at least one individual organ score is non-missing, the individual organ scores will be imputed using last observation carried forward. In this case, it is possible that different components come from different visits. This will not be done at Day 21 and Day 28.

The following will defined mSOFA LOCF.

- 3. If all organ scores are missing on Day 14 or earlier, the mSOFA total score from that day will be imputed using last observation carried forward with the following exception..
 - c. LOCF will not be performed after patient death.
 - d. Note that LOCF will not be performed for unavailable mSOFA total scores at Day 21 and Day 28.
- 4. When summarizing the individual organ scores apart from the mSOFA total scores, the same rules as above will apply.

Since LOCF will not be applied to missing mSOFA scores after patient death in analyses that employ LOCF to describe mean values of time, there may be some 'diminishing n' and focus is therefore on morbidity rather than mortality.

In contrast, the mixed model repeated measures analyses (MRMM) will utilize implicitly imputed values for all missing values including those subsequent to patient death.

In categorical analyses including formulation of the primary efficacy endpoint, an mSOFA value that is greater than 1 at Day 14 is considered a primary treatment failure in the same fashion as patient death at any time throughout the 28 day follow-up period. LOCF for SOFA is necessary to guarantee that every patient has a value at Day 14 for use in determining NICCE among patients that are alive at the Day 28 and who have not otherwise failed due to other NICCE components including more than 3 debridements, amputation beyond the first debridement.

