1. If a single individual organ score is missing but other scores for that day are non-missing, the organ system that were not evaluated are assumed to be free of organ failure and are given a value of zero when determining the sum score.

⁸ Vincent JL, Moreno R, Takala J, et al: The SOFA (Sepsis-related Organ Failure Assessment) score to describe organ dysfunction failure: On behalf of the Working Group on Sepsis-Related Problems of the European Society of Intensive Care Medicine. Intensive Care Med 1996; 22:707–710.

⁹ Vincent JL, Angus DC, Artigas A, Kalis A, Basson BR, Jamal HH, Johnson III G., Bernard GR for the PROWESS Study Group. Effects of drotrecogin alfa (activated) on organ dysfunction in the PROWESS trial. Crit Care Med 2003; 31:834 – 840.

2. If two or more individual organ scores are missing for mSOFA on Day 14 or earlier, but at least one individual organ score is non-missing, the individual organ scores will be imputed using last observation carried forward. In this case, it is possible that different components come from different visits. This will not be done at Day 21 and Day 28.

The following will defined mSOFA LOCF.

- 3. If all organ scores are missing on Day 14 or earlier, the mSOFA total score from that day will be imputed using last observation carried forward with the following exception.
 - a. LOCF will not be performed after patient death.
 - b. Note that LOCF will not be performed for unavailable mSOFA total scores at Day 21 and Day 28.
- 4. When summarizing the individual organ scores apart from the mSOFA total scores, the same rules as above will apply.
- 5. Patients with recorded screening mSOFA inflated by GCS scores due to mechanical ventilation or due medications will have their GCS score removed when determining screening mSOFA. This is to prevent subjects meeting trial inclusion just on the basis of GCS.

Since LOCF will not be applied to missing mSOFA scores after patient death in analyses that employ LOCF to describe mean values of time, there may be some 'diminishing n' and focus is therefore on morbidity rather than mortality.

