Specifically, MMRM will be used to compare mean values at each time point between the Reltecimod 0.50 mg/kg dose and placebo with a key emphasis on the Day 14 contrast. Model parameters will be estimated using Restricted Maximum Likelihood¹⁹,²⁰(REML) as implemented Proc Mixed [SAS Institute²¹]. A generalized Satterthwaite approximation will be used to determine accurate estimates of denominator degrees of freedom for statistical tests²². Analyses will characterize changes over time as functions of the baseline value, treatment group, time, and treatment by time interaction. Between-group differences at each time point will be evaluated using contrasts derived from mixed model parameter estimates. This approach produces inferences that are valid under the assumption of 'missing at random' (MAR). MAR based inferences are valid under broader assumptions than complete case analysis or analyses utilizing LOCF²³. The modeling results will be graphically presented by plotting the individual least squares predicted mean values.

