5.10.3 Mixed Model Repeated Measures

The use of MMRM is another method used to address missing data and is considered an optimal approach in many settings. The use of MMRM results in implicit imputations for missing data which are valid under missing at random (MAR), a more general set of assumptions than 'missing completely at random (MCAR)'. For these analyses, there will be implicit imputation of expected mSOFA after patient death. Methods assuming Not Missing at Random (NMAR) require extensive modelling and sensitivity analyses regarding inherently untestable assumptions concerning the missingness mechanism; and will not be used in these analyses.

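### No comparison of the Day 14 mSOFA score itself counts death: the score summaries omit patients who died, and the supporting MMRM imputes a score for them

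*SAP*

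**What the plan says.** SAP 5.2 and 5.10.1 list four ways of assessing mSOFA: observed cases, LOCF, MMRM, and the score "categorized and combined with mortality and local activity as part of the primary composite clinical success endpoint, NICCE". They treat death differently.

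- **Observed cases and LOCF.** The LOCF rule carries the exception that "LOCF will not be performed after patient death". The SAP concedes that "there may be some 'diminishing n' and focus is therefore on morbidity rather than mortality". SAP 8.6 presents these results as tables, line plots and box plots, and names no between-group test for them.
- **MMRM.** SAP 5.10.1 says that it "will utilize implicitly imputed values for all missing values including those subsequent to patient death", and SAP 5.10.3 repeats that "there will be implicit imputation of expected mSOFA after patient death". SAP 5.8 compares means at each time point "with a key emphasis on the Day 14 contrast". SAP 5.2.4 and 5.8 call the analysis supporting. On alternatives, SAP 5.10.3 says that "Methods assuming Not Missing at Random (NMAR) require extensive modelling and sensitivity analyses regarding inherently untestable assumptions concerning the missingness mechanism", and rules them out.
- **Categorical analyses, including NICCE.** A Day 14 mSOFA above 1 and death are both failures (SAP 5.10.1).
- **Day 14 time to resolution.** Patients who die before Day 14 stay in the analysis as never having reached mSOFA ≤1, and a log-rank test is used (SAP 8.7).

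The Day 14 mSOFA distribution is a listed secondary endpoint (SAP 4.2). SAP 5.6 makes no attempt to control type 1 error for secondary endpoints other than the key AKI endpoint.

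**The concern.** A patient who dies before the Day 14 assessment has no organ function to score. If sicker patients die more often on one arm, that arm's survivors are a healthier selection, and its mean score falls for a reason unrelated to organ recovery. The reverse also holds: an arm that keeps very sick patients alive keeps their high scores in its mean.

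SAP 4.3 makes this argument itself. It warns that outcomes such as ventilation time and incidence of organ failure can look lower in the arm with higher mortality, and it answers with free-day outcomes that give no credit for days after death. Organ failure is what mSOFA measures, yet the mSOFA score gets no such treatment. Saying that the "focus is therefore on morbidity rather than mortality" (SAP 5.2) discloses the limitation but does not remove it.

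At stake is how one listed secondary endpoint and its supporting analyses are read if mortality differs by arm.

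**Working it through.** **1. The plan's own figures.** The documents give no power or sample size for any mSOFA score comparison. The nearest stated figures are for NICCE, the mSOFA-based analysis that counts death. With 145 per arm, two-sided α = 0.01 and rates centred on 0.5, a pooled-variance chi-square calculation gives 99.6%, 95.9% and 80.2% for differences of 0.30, 0.25 and 0.20. SAP 2.4.1 states 99%, 95.9% and 80.2%. For 0.60 vs 0.40:

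- null SE = √(2 × 0.5 × 0.5/145) = 0.0587, so the critical difference is 2.576 × 0.0587 = 0.1513
- alternative SE = √(0.48/145) = 0.0575
- power = Φ((0.20 − 0.1513)/0.0575) = Φ(0.847) = 80.2%

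The co-primary figures, 96.4% and 84.8%, also reproduce. This point changes none of them.

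**2. Survivors-only means.** Let dP and dD be mortality by Day 14 on placebo and drug, m0 the mean score of patients who survive on either arm, and mr the mean score of patients saved only by drug. Assume that the drug has no effect on scores. Then

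drug mean − placebo mean = [(1 − dP)·m0 + (dP − dD)·mr]/(1 − dD) − m0 = (dP − dD)(mr − m0)/(1 − dD).

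Inputs:
- Mortality of 20% vs 6.7% is Phase 2 placebo vs 0.5 mg/kg (Protocol 1.1.3.3.2, Table 3).
- 17% is the upper literature rate in Protocol 1.1.1. The 10% drug-arm rate and the 15% vs 10% pair are assumptions.
- m0 of 1.0 to 1.5 and mr of 4 to 8 are assumptions.

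| Placebo / drug mortality | (dP − dD)/(1 − dD) | m0 1.5, mr 4 | m0 1.0, mr 8 |
|---|---|---|---|
| 20% / 6.7% | 0.133/0.933 = 0.1426 | × 2.5 = +0.36 | × 7 = +1.00 |
| 17% / 10% | 0.07/0.90 = 0.0778 | × 2.5 = +0.19 | × 7 = +0.54 |
| 15% / 10% | 0.05/0.90 = 0.0556 | × 2.5 = +0.14 | × 7 = +0.39 |
| 17% / 17% | 0 | 0 | 0 |

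A positive value means that the drug looks worse although it only saved lives. Swapping the arms gives the same sizes in the drug's favour when the drug arm has the excess deaths.

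**3. Counting death restores the direction.** Take 20% vs 6.7%, m0 = 1.5, mr = 6, and score death at 20 (five organs × 4). Placebo: 0.80 × 1.5 + 0.20 × 20 = 5.20. Drug: 0.80 × 1.5 + 0.133 × 6 + 0.067 × 20 = 3.34. A rank test needs only the ordering, not the value 20.

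**4. The MMRM.** Step 2 does not describe a model that uses scores recorded before death. A small simulation (100 trials, 145 per arm, all deaths before Day 14, one latent severity driving both death and score, no drug effect on scores) compared observed cases with a multivariate-normal MAR model without the SAP's covariates:

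| Mortality | Observed cases | MMRM-type | P(drug better), death worst | mSOFA ≤1, death = failure |
|---|---|---|---|---|
| 20% / 6.7% | +0.15 | +0.01 | 0.54 | +4.9 points |
| 17% / 10% | +0.10 | +0.04 | 0.52 | +1.9 points |

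The MMRM-type shift is close to zero because pre-death scores carry information about the later course. With 100 trials, the gap between +0.01 and +0.04 should not be interpreted. The observed-case shifts here lie below the ranges in step 2 for the same mortality pairs, so the size depends heavily on the score model assumed.

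**The case against.** The strongest reply is that this is a disclosed choice of estimand. The SAP says that these summaries describe morbidity, reports survival separately (SAP 8.1 and 9.6), and leaves the analyses descriptive. That stands, and it limits the importance of the point. It does not explain why SAP 4.3 offers a remedy for competing mortality elsewhere and none for this score.

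Four stronger readings are tempting, and the documents do not support them.

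- A reader might infer that no mSOFA analysis counts death. NICCE and the Day 14 time-to-resolution analysis do. For the stand-alone component of Day 14 mSOFA ≤1 the SAP gives no separate rule for deaths, but its sentence on categorical analyses points to failure.
- A reader might take the MMRM Day 14 contrast as the main test of the distribution endpoint. SAP 5.7 does base testing of mSOFA over time on the MMRM, but the SAP calls it supporting, reports it in two line figures (SAP 8.8), and nowhere makes it the test of that endpoint. The Day 14 emphasis ranks time points within the model.
- A reader might apply the 0.2 to 1.0 point shift to the MMRM. It belongs to survivors-only means.
- A reader might expect a reversal in this trial. In Phase 2 the 0.5 mg/kg arm had both lower mortality and a lower Day 14 SOFA (0.7 vs 2.7), although the protocol does not say how deaths were handled there.

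It is also fair that only deaths before the Day 14 assessment remove a Day 14 score. The documents give no Day 14 mortality, so using total mortality overstates the number missing.

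**Conclusion.** The point holds for comparisons of the mSOFA score itself. Observed-case and LOCF means, changes and box plots at Day 14 are conditional on survival. The MMRM estimates a hypothetical mean that includes patients who have died. No sensitivity analysis ranks death as worst.

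For survivors-only means, the illustration gives about 0.2 to 1.0 points against an arm that only saves lives, at mortality of 20% vs 6.7% or 17% vs 10%. It is smaller for smaller gaps and zero at equal mortality. It rests on assumed scores, on mortality figures taken as if they applied by Day 14, and on no drug effect on the score. For an MMRM-type model the simulated shift is slight; what remains there is the meaning of the estimate, not a demonstrated reversal.

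Study success, which rests on NICCE and the conditional co-primary endpoint (SAP 2.2), is untouched. This is a cheap improvement, not a defect in the primary analysis.

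**What to change.** In SAP 5.2, 5.10.1 and 8.6, name one between-group test for the Day 14 mSOFA distribution endpoint: a Wilcoxon rank-sum test with c-statistic in the mITT set, with all patients dead by the Day 14 assessment tied at the worst rank. Patients alive without a Day 14 score keep the existing LOCF rule. Both tools are already in the SAP for the critical-care endpoints (5.7 and 8.9), and the p-value stays nominal.

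Label the observed-case and LOCF summaries as conditional on survival. Label the MMRM as a hypothetical estimand that imputes scores after death; calling it a description of survivors would be wrong.

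The cost is a row in an existing table (Table 14.2.2.2 is the natural place) and some SAP wording. No new data are needed, and SAP section 1 provides for finalisation before the allocation codes are unblinded. The downside is that the ranked score mixes morbidity with mortality, as NICCE already does, so it should be read beside the survival-conditional summaries.
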